9.11.2 Vital Signs

For each of the vital signs, summary statistics of observation and the change from baseline will be presented by treatment group for each scheduled time point. Baseline is defined as the last value obtained before the initiation of the study treatment.

9.11.3 Clinical Laboratory Analysis

For each of laboratory tests, summary statistics of observation and the change from baseline will be presented by treatment group for each scheduled time point. Baseline is defined as the last value obtained before the initiation of the study treatment.

Qualitative laboratory test data at baseline and at scheduled time point will be classified according to test category, and the frequency of each pair will be presented in a 2-dimensional contingency table by treatment group.

9.11.4 Electrocardiography

Electrocardiography will be performed to assess the presence of acute conditions that may exclude patients or conditions in the opinion of the investigator that may be considered AEs during the study. The frequency of ECG findings will be summarized by treatment group.

9.12 Pharmacokinetic Analysis

Plasma S-033447 concentration data will be plotted against the actual sampling time to determine the PK of S-033447. Plasma S-033447 concentration 24 hours (acceptable time window: 20 to 28 hours) postdose (C₂₄) will be listed and summarized with the number of non-missing observations (N), arithmetic mean (Mean), standard deviation (SD) and coefficient of variation (CV%, calculated by SD/Mean × 100), geometric mean (Geometric Mean) and coefficient of variation for geometric mean (CV% Geometric Mean, calculated by [exp (sd²)–1]^{1/2} × 100, where SD is the standard deviation for natural log [ln]-transformed data), median, minimum, and maximum values. C₂₄ will be plotted against body weight.

Specification of PK parameters for analysis, statistical level of significance to be used, procedures for accounting for missing, unused or spurious data, procedures for reporting deviations from the original statistical plan, and selection of patients to be included in the analysis populations will be presented in the PK analysis plan or PK analysis report as appropriate.

PK parameters reported will be detailed in the PK analysis plan. Other parameters may be added if deemed appropriate. If needed, the relationships between the C_{24} and the efficacy endpoints may be assessed across dose groups. The PK/pharmacodynamic (PD) analysis for each efficacy endpoint will include all patients who have the value of C_{24} and each evaluable PD assay result.

9.13 Other Analyses

9.13.1 Serum Influenza Antibody Titer

Serum influenza antibody titers measured at Visit 1 (Day 1) and Visit 7 (Day 22) will be categorized, and the frequency of each category will be tabulated by treatment group. The ratio of value at Visit 7 to that at Visit 1 will be categorized, and the frequency of each category will be tabulated by treatment group. For the ratio (Visit 7/Visit 1), the geometric mean value will also be calculated, and the S-033188 group will be compared with the placebo group regarding the geometric mean ratio, using the Wilcoxon rank sum test.

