- Requirement for systemic antibiotics for infections secondary to influenza infection
- Incidence of influenza-related complications (hospitalization, death, sinusitis, bronchitis, otitis media, and radiologically confirmed pneumonia)
- Intrahousehold infection rate (for Japan only)

Other Endpoints:

- Serum influenza antibody titer
- Polymorphic and treatment-emergent amino acid substitutions in the PA gene
- Drug susceptibility in patients with evaluable virus
- Health Economic Outcomes
 - _ CPI
 - WP questionnaire

Safety Assessments:

Frequencies of adverse events (AEs), serious AEs, vital sign measurements, physical examinations, electrocardiography (ECGs), and clinical laboratory tests

Pharmacokinetic Assessments:

For the measurement of plasma S-033447 concentrations, blood samples will be collected at Visits 2 (Day 2) and 4 (Day 5). If circumstances permit, samples will also be collected at 0.5 to 4 hours postdose at Visit 1 (Day 1), at Visits 3 (Day 3) and 6 (Day 15).

Statistical Methods:

The intention-to-treat infected (ITTI, defined as RT-PCR positive for influenza) set will be the primary efficacy analysis population in the study. The per-protocol set (PPS) will be used to support the primary analyses for efficacy. Statistical testing will be performed at the 2-sided significance level of 0.05 unless stated otherwise.

Primary Efficacy Analysis:

The primary efficacy analysis will be performed on the primary endpoint, the time to improvement of influenza symptoms, by comparing S-033188 and placebo using the stratified generalized Wilcoxon test with composite symptom scores at baseline, preexisting and worsened symptom at baseline, and region as stratification factors.

Furthermore, the Kaplan-Meier curves will be plotted for each treatment group, and the median time to improvement of symptoms and its 95% confidence interval will be calculated. The same analysis in the PPS will be performed as a sensitivity analysis.

Secondary Efficacy Analysis for Primary Endpoint:

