5.4 Method of Assigning Patients to Treatment Groups

Each patient who is qualified for entry in the study will be randomized to S-033188, oseltamivir, or placebo in a ratio of 1:1:1. An interactive web response system (IWRS) will be used to assign patients to numbers for which treatment has already been randomly assigned. The randomization will use the stratified randomization method for balancing the following 4 factors: baseline symptom score ($\leq 14, \geq 15$), preexisting and worsened symptom (Yes, No: if a patient has at least 1 of 3 symptoms [namely cough, muscle or joint pain, or fatigue] that is preexisting and worsened, the patient will be assigned to the 'Yes' category , otherwise 'No'), region (Asia, North America/Europe, southern hemisphere), and weight (< 80 kg, \geq 80 kg). The registration center manager will prepare and complete the randomization procedures/processes.

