7.7 Other Assessments

7.7.1 Serum Influenza Antibody Titer Test

Blood samples will be collected predose at Visit 1 (Day 1) and Visit 7 (Day 22). Specimens will be handled according to Section 7.6.4.5.

The clinical laboratory will measure serum antibody titers for the influenza A and B viruses.

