9. PLANNED STATISTICAL METHODS

9.1 General Considerations

The statistical analysis and PK analysis will be performed by the sponsor or a designee. The detailed statistical analysis methods will be specified in a statistical analysis plan (SAP) and PK analysis plan according to this section of the study protocol. If analyses deviated from those outlined in the protocol, the reason for deviation from the protocol will be described in the SAP and PK analysis plan. The SAP and PK analysis plan will be finalized before scheduled unblinding.

Unless otherwise noted, continuous variables will be summarized by using the number of nonmissing observations, arithmetic mean, standard deviation, median, minimum, and maximum values as descriptive statistics; categorical variables will be summarized by using the frequency count and the percentage of patients in each category as descriptive statistics.

All statistical tests will be performed at the 0.05 significance level using 2-sided tests, except where otherwise noted. The primary endpoint will first be compared between the S-033188 and placebo groups for patients (primary analysis). Together with the primary efficacy analysis, a comparison between the S-033188 group and the oseltamivir group (secondary analysis) will be conducted in a hierarchical manner so as to maintain control of overall type I error. For Japan, control of overall type I error is not required for the secondary efficacy analysis of the primary endpoint. All patient study data will be presented in listings. In general, all tables will be presented by treatment group. Individual patient data will be presented by treatment and by patient. All analyses and tabulations will be performed by using both SAS[®] Version 9.2 or higher and WinNonlin[®] Version 6.2.1 or higher.

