The required sample size will therefore be calculated based on the conservative assumption of a 36-hour difference (assuming that the median time to improvement of influenza symptoms in the placebo group and the S-033188 group was 150 and 114 hours, respectively) in the median time to improvement of influenza symptoms between the S-033188 group and the placebo group to ensure at least 90% power in the efficacy evaluation of S-033188.

Patients will be randomized on a 1:1 basis to either S-033188 or placebo and a follow-up period will be 336 hours (14 days). Assuming that the time follows an exponential distribution, the study will require 790 patients in the ITTI population in order for the generalized Wilcoxon test to have 90% or more power with a 2-sided significance level of 5% (395 patients in the S-033188 group and placebo group, respectively).

Using a 1:1 randomization ratio between the S-033188 group and the oseltamivir group, the ITTI population of oseltamivir will be 395 patients. Table 9-1 shows the statistical power to compare between the S-033188 group and the oseltamivir group under several sets of assumed time to improvement of influenza symptoms.

Table 9-1	Statistical Power to Compare Between S-033188 and
	Oseltamivir

Median Time to Alleviation of Symptoms (S-033188, Oseltamivir)	Statistical Power for Comparison Between S-033188 and Oseltamivir by Generalized Wilcoxon Test
(114 hours, 126 hours)	22.3%
(108 hours, 126 hours)	45.3%
(102 hours, 126 hours)	71.5%
(96 hours, 126 hours)	90.2%

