9.10.3.2 Analyses of Secondary Endpoints

1) Proportion of patients positive for influenza virus titer and proportion of patients positive by RT-PCR at each time point

Only patients whose virus titer/RT-PCR predose at Visit 1 are \geq the lower limit of quantification will be included in the analyses. The summary table by each time

point will be made. The Mantel-Haenszel test at each time point will be used to compare the proportion of patients with positive virus titer/RT-PCR between S-033188 and oseltamivir/placebo with baseline symptom score ($\leq 14, \geq 15$), preexisting and worsened symptom (Yes, No), and region (Asia, North America/Europe, Southern Hemisphere) as stratification factors.

2) Change from baseline in virus titer and the amount of virus RNA (RT-PCR) at each time point

Only patients whose virus titer/RT-PCR predose at Visit 1 are \geq the lower limit of quantification will be included in the analyses. The van Elteren test will be used by each time point to compare the S-033188 with oseltamivir/placebo, where baseline symptom score ($\leq 14, \geq 15$), preexisting and worsened symptom (Yes, No), region (Asia, North America/Europe, Southern Hemisphere) will be included as stratification factors. Summary statistics will be calculated by time point and by treatment group.

3) AUC adjusted by baseline in virus titer and in the amount of virus RNA (RT-PCR)

Only patients whose virus titer/RT-PCR predose at Visit 1 are \geq the lower limit of quantification will be included in the analyses. The same statistical methods as 2) change from baseline in virus titer and the amount of virus RNA (RT-PCR) at each time point will be used. Summary statistics will be calculated by treatment group.

4) Time to cessation of viral shedding by virus titer and by RT-PCR

Only patients whose virus titer/RT-PCR predose at Visit 1 are \geq the lower limit of quantification will be included in the analyses. The same analyses as the primary endpoint will be performed.

5) Proportion of patients whose symptoms has been alleviated at each time point

The same analyses as 1) proportion of patients positive for influenza virus titer and proportion of patients positive by RT-PCR will be used.

6) Time to alleviation of symptoms

The same analyses as the primary endpoint will be performed.

 Time to improvement in the 4 systemic symptoms (headache, feverishness or chills, muscle/joint pain, and fatigue)

The same analyses as the primary endpoint will be performed.

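### The antibody analysis pairs a geometric mean ratio with an unstratified rank sum test that compares fold-rise distributions, and it does not adjust for the Visit 1 titer

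*Protocol*

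**What the plan says.** Protocol Section 9.13.1 tabulates categorized titers and categorized ratios by group. It then adds: "For the ratio (Visit 7/Visit 1), the geometric mean value will also be calculated". The next clause names the contrast and the test: "the S-033188 group will be compared with the placebo group regarding the geometric mean ratio, using the Wilcoxon rank sum test". No stratification factor and no covariate is named.

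Four other parts of the protocol bear on this:

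- Section 7.7.1 makes the Visit 1 sample a predose sample, so the denominator of the ratio is the baseline titer.
- Section 5.4 says: "The randomization will use the stratified randomization method for balancing the following 4 factors". The factors are baseline symptom score, preexisting and worsened symptom, region, and weight.
- Section 9.10.3.2, item 2, handles change from baseline in virus titer and viral RNA with the stratified form of the same rank test: "The van Elteren test will be used by each time point to compare the S-033188 with oseltamivir/placebo". It uses three of the four randomization factors, leaving out weight.
- The synopsis lists antibody titer among the other endpoints. Under Section 9.1 the hierarchical testing covers only the two comparisons of the primary endpoint.

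**The concern.** A geometric mean is one number per group. A rank sum test asks whether values in one group tend to exceed those in the other. The sentence in Section 9.13.1 presents the second as a test of the first. If the two fold-rise distributions differ in shape, for example because one group splits into responders and non-responders, the p-value and the reported estimate answer different questions. A small p-value could then stand beside geometric means that do not differ, or the reverse.

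Two lesser points follow from the same sentence. The test leaves out strata that the protocol uses for its closest parallel. The Visit 1 titer, already measured, enters only as a denominator, which fixes its slope on the log scale at 1 and does not let the data estimate it. Both can cost precision.

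**Working it through.** **Is there a figure to reproduce?** The protocol gives no power, effect size or variance for the antibody analysis. The 395 per group used below is the Section 9.2 figure for the infected population, taken only to size the illustration. That figure does reproduce. With exponential times, censoring at 336 hours and two-sided 0.05, 395 per group gives 90.0% power for medians of 150 and 114 hours. The four powers in Table 9-1 come out at 22.2, 45.3, 71.5 and 90.2%, against 22.3, 45.3, 71.5 and 90.2% stated. Nothing below depends on this.

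**What the rank sum test responds to.** Simulation of 3,000 trials, 395 per group, two-sided 0.05, on log2 fold-rise. All distributions are assumptions. The comparator is a Welch t-test on the log ratio, which does test geometric means.

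| Scenario | Rank sum rejects | t-test on log ratio rejects |
|---|---|---|
| Identical normals (mean 2, SD 1.5) | 4.8% | 4.7% |
| Pure shift of 0.3 (SD 1.5) | 77.8% | 79.4% |
| Equal geometric means: normal (2, SD 1.5) vs responder mixture | 16.7% | 4.9% |
| Equal geometric means: normal (2, SD 1) vs exponential (mean 2) | 98.9% | 5.2% |

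The mixture row can be checked by hand. The mixture is 30% normal with mean 4.1 and 70% normal with mean 1.1, each with SD 1. Its mean is 0.3 × 4.1 + 0.7 × 1.1 = 2.0, equal to the comparison group.

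- The SD of a difference between one patient from each group is √(1² + 1.5²) = 1.803.
- The probability that a mixture patient exceeds a comparison patient is 0.3 × Φ(2.1/1.803) + 0.7 × Φ(−0.9/1.803) = 0.3 × 0.878 + 0.7 × 0.309 = 0.480, not 0.5.
- The null standard error of that probability is √[791/(12 × 395²)] = 0.0205.
- The shift is about 0.020/0.0205 ≈ 1 standard error, so rejection is about 17%, as simulated.

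**Leaving out strata.** Two-level stratum exactly balanced in both groups, outcome SD 1 within stratum, true shift 0.2 SD:

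| Stratum effect (SD) | Null rejection | Power |
|---|---|---|
| 0 | 4.9% | 79% |
| 0.5 | 4.3% | 76% |
| 1 | 3.3% | 71% |
| 2 | 0.5% | 44% |

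The effect is conservatism and lost power.

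**Ratio against baseline adjustment.** Let s1 and s7 be the SDs of log titer at Visits 1 and 7, and r their correlation.

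- Variance of the log ratio: s1² + s7² − 2·r·s1·s7.
- Residual variance from ANCOVA: s7²(1 − r²).
- Difference: (s1 − r·s7)², which is never negative. In large samples ANCOVA is therefore never less precise.
- With s1 = s7, the variance ratio is (1 − r²)/[2(1 − r)] = (1 + r)/2. For an assumed r of 0.3 to 0.7 this is 0.65 to 0.85.
- With s1 = r·s7, the difference is zero, the ratio is 1.0 and there is no gain.

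The protocol gives none of r, s1 or s7.

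**The case against.** The strongest defence is that the test is valid and ordinary. Ranks do not change under a log transform, so testing the ratio and testing the log ratio by rank sum are the same. If the groups differ by a log-scale shift, the test bears on geometric means with almost no power loss, and its size is correct when the distributions are identical. The 16.7% and 98.9% depend on assumed shapes that nothing in the protocol supports. All of this stands. It limits the size of the problem but does not make the sentence right, because the protocol does not state the shift assumption.

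A second defence is that covariates, strata and intervals belong in the SAP. For the interval alone, that is fair. But Sections 9.13.2, 9.13.3, 9.13.4.2 and 9.13.5 leave their methods to the SAP, while Section 9.13.1 names the summary, the contrast and the test. Section 9.1 says that the SAP follows this section and must give reasons for departures.

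Several stronger readings are tempting, and the documents do not support them:

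- That the baseline titer is unused. It is the denominator; what is absent is adjustment for it.
- That this analysis alone lacks strata. The Fisher's exact tests for antibiotic use and complications (Section 9.10.3.2, items 14 and 15) are unstratified too. The sound comparison is with the van Elteren analysis in item 2.
- That omitting strata inflates type I error. The simulation shows the opposite.
- That ANCOVA gives a known gain over the plan. The range 0.65 to 0.85 assumes equal variances and a value of r, and it compares ANCOVA with a parametric analysis of the log ratio that the plan does not contain.
- That the trial is meant to show whether rapid viral clearance weakens the antibody response. No objective in Sections 2.1 to 2.6 mentions antibody titer.

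**Conclusion.** The point holds as a minor one. Section 9.13.1 states a comparison of geometric means and names a test that compares fold-rise distributions. The two agree only under a pure log-scale shift. The named test also leaves out the strata used for the parallel virology analysis, and it does not adjust for a baseline titer that is already collected.

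The mismatch itself needs no assumption. Its practical size does: it ranges from negligible under a log shift to severe under marked shape differences, and the protocol gives no titer distribution to choose between them. The precision lost by not adjusting for baseline also cannot be fixed from the document. The variance ratio is 0.65 to 0.85 with equal variances and r between 0.3 and 0.7, and it can reach 1.0. No conclusion on the primary endpoint or in the hierarchical testing is affected.

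**What to change.** Preferred: analyze log Visit 7 titer by ANCOVA with treatment, log Visit 1 titer, and the three stratification factors used in Section 9.10.3.2. Report the adjusted geometric mean ratio of S-033188 to placebo with its 95% CI and p-value, and keep the categorical tables. ANCOVA is already used for body temperature in Section 9.10.3.2, item 11.

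Minimum: describe the test as a comparison of the distributions of fold-rise, and use the van Elteren test with the strata of Section 9.10.3.2, item 2. The geometric mean ratio then remains as a descriptive summary.

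The cost is a change of wording and one model, with no new data. The price of the preferred option is reliance on a log-normal model for titers that may be censored at the assay limit. If censoring is heavy, the van Elteren version is a reasonable companion analysis.

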9.13.2 Polymorphic and Treatment-emergent Amino Acid Substitutions in the PA Gene

This analysis will be conducted for the patients in the S-033188 and placebo groups and the methodological details will be specified in the SAP.

9.13.3 Drug Susceptibility Testing for Test Substances

This analysis will be conducted for all patients and further details will be specified in the SAP.

9.13.4 Health Economic Outcomes

9.13.4.1	CPI	and ^{CPI}	
The combin	nation of the CPI	and the CPI	will be presented as:

- change in the index value from baseline to each time point
- change in the CPI from baseline to each time point

9.13.4.2 Work Productivity Questionnaire

Analysis variables and analysis methods will be specified in the SAP.

9.13.5 Intrahousehold Infection Rate

The definition of the endpoint and the analysis method for the endpoint will be specified in the SAP.

9.14 Interim Analysis

No interim analysis is planned for this study. If the study extends beyond 1 Northern Hemisphere influenza season, an interim analysis may be considered.

10. ADMINISTRATIVE CONSIDERATIONS

[figure not shown]

10.2 Institutional Review Board or Independent Ethics Committee Approval

The IRB/IEC will safeguard the rights, safety, and well-being of the patients by reviewing the following study documents: the protocol, Informed Consent Form, written information on patient recruitment procedures (if applicable), other written information given to the patients, Investigator's Brochure, safety updates, annual progress reports (if applicable), and any significant revisions to these documents. The investigator or the sponsor will provide these study documents to the IRB/IEC. The IRB/IEC will be appropriately constituted in accordance with ICH GCP, and local requirements, as applicable. The study will be undertaken only after the IRB/IEC has given full approval and the investigator has received a document being approved.

Amendments to the protocol will be subject to the same requirements as the initial review. The investigator will submit all periodic reports and updates as required by the IRB/IEC. The investigator will inform the IRB/IEC of any reportable AEs.

10.3 Ethical Conduct of the Study

The study will be conducted in accordance with all appropriate regulatory requirements and under protocol approved by the IRB/IEC. The study will be conducted in accordance with current ICH GCP, all appropriate patient privacy requirements, and the ethical principles that are outlined in the Declaration of Helsinki.

10.4 Patient Information and Consent

The investigator will generate an informed consent form for the study. The sponsor will provide the investigators with a proposed informed consent form that complies with the ICH GCP and regulatory requirements. The consent form will include all the elements required by the ICH GCP and any additional elements required by local regulations and will be reviewed and approved by the appropriate IRB/IEC before use. The sponsor must agree to any changes to the proposed consent form suggested by the investigator prior to submission to the IRB/IEC, and the IRB/IEC approved version must be provided to the site monitor after IRB/IEC approval.

The investigator or subinvestigator will explain the nature, purpose, methods, reasonable anticipated benefits, and potential hazards of the study to the patient in simple terms by using the consent form approved by the IRB/IEC before the patient is entered into the study. The method of obtaining and documenting informed consent will comply with ICH GCP and all applicable regulatory requirements.

